10.19 Daily Spasm Count

The 7-day average daily spasm count will be derived for each patient using the number of spasms recorded in the eDiary during the last 7 days preceding Period 1 Day 1 H0 (Baseline), and Day 15 and D21 of each treatment period as follow:

$$\frac{\text{Total spasm count during the 7 - day period}}{\text{Number of days in which the daily diary was completed during the 7 - day period}}$$

For each analysis timepoint, the 7-day average daily spasm count will be set to missing if spasm counts are not collected during 4 days or more in total or for 3 consecutive days during the 7-day period.

In case of the diary data are available but the visit does not take place the target visit date will be used.

On-treatment / off-treatment assessment

A 7-days average daily spasm count will be considered on-treatment if derived using only post-baseline daily records collected on or before the date of IMP discontinuation and will be considered off-treatment otherwise.

In case of IMP discontinuation, if possible with regards to missing data rule specified just above, the 7-day average daily spasm count considered on-treatment will also be derived using only post- baseline spasm counts collected on or before the date of IMP discontinuation.

Missing daily spasm count information

If for a given day, the spasm count is missing whereas the eDiary has been filled by the patient, the number of spasms will be imputed to "0" to derive the 7-days average daily spasm count.

The change from baseline will then be calculated (as respectively described in [Section 10.3](#)).

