10.8.2 Number of Sprays Summary

For each parameter presented in this section,

- **The start and stop date** of each studied period is defined in [Section 10.8.1](#). These studied periods are defined for Period 1 and Period 2 to allow summaries by treatment arm.
- **The duration of each studied period** will then be derived using the appropriate treatment phase (titration, maintenance) for each treatment period as: Date of stop – date of start + 1 day
- eDiary information will be used to retrieve the total daily number of sprays taken by a given patient
- A **non-missing diary day** is defined as any day where the eDiary is filled but IMP dosing information are fully included or partial (missing morning or evening dose) or totally missing.
- A **missing diary day** is defined as any day where the eDiary is not filled
- **Imputation rule:** for a non-missing diary day where IMP dosing information is partial or missing the number of sprays taken on that missing morning or evening administration will be imputed to "0" to derive the total daily number of spray taken.

The mean number of sprays is defined for each treatment arm as the total number of sprays taken during the studied period divided by the number of patients within the studied period regardless intermittent IMP discontinuation.

The patient mean number of daily sprays a patient has taken on a daily basis is calculated for each studied period as the total number of sprays taken divided by the number of non-missing diary days for each patient.

Based on the above the patient mean number of daily sprays (also called mean use of IMP) will also be categorized as follows:

- ≤ 6 sprays,
- > 6 sprays and ≤ 12 sprays,
- > 12 sprays.

The total number of daily sprays is referring to the total number of sprays a patient has taken on a daily basis for a studied period.

The patient median number of daily sprays refers to is referring to the median number of sprays a patient has taken on a daily basis for a studied period.

The patient mode number of daily sprays refers to more frequently occurring number of sprays a patient has taken on a daily basis for a studied period. If a patient has more than one mode or no mode determined then the patient has a 'missing' mode.

The patient maximal number of daily sprays refers to the maximal number of sprays a patient has taken on a daily basis for a studied period.

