10.17 Timed 25-Foot Walk

The T25FW is the time needed for a patient to walk 25-feet and will be performed at Day 1 H0 and D21 of each treatment period. The test consists of two trials separated by a 5-minute rest period. The maximum duration of each trial is set to 3 minutes (180 seconds).

The average T25FW (expressed in seconds) will be derived for each patient as the average of the two trials..

If a patient only performs 1 of the 2 trials at a given analysis day, the unperformed trial will be imputed using the highest T25FW (180 seconds) to perform the main analysis. An exploratory analysis will also be conducted without imputing unperformed trial as missing thus, leading to a missing average T25FW.

If a patient is not using the same device or is introducing a device within a given treatment period, the average T25FW will be set to missing.

The change and percentage change from baseline will then be calculated (as respectively described in [Section 10.3](#) and in [Section 10.4](#)).

The percentage change from baseline will be categorized as $\leq -20\%$ and $> -20\%$ to assess respectively $\geq 20\%$ improvement (as response) and $< 20\%$ improvement (as non-response) using imputed T25FW (as described above).

Missing average T25FW will be considered as not having met the improvement criteria (imputed as failure).

10.18 11-point Numerical Rating Scale Score (NRS-Spasticity Score)

The 7-day average 11-point NRS spasticity score will be derived for each patient as the mean NRS-spasticity score recorded in the eDiary during the last 7 days preceding Period 1 Day 1 H0 (Baseline), and Day 15 and D21 of each treatment period as follows:

Sum of the NRS spasticity scores during the 7 – day period

Number of days in which the daily diary was completed during the 7 – day period

For each assessment timepoint, the 7-day average 11-point NRS-spasticity score will be set to missing if scores are missing for 4 days or more in total or for 3 consecutive days within each 7-day period.

In case of the diary data are available but the visit does not take place the target visit date will be used.

On-treatment / off-treatment assessment

A 7-day average 11-point NRS spasticity score will be considered on-treatment if derived using only post baseline daily scores collected on or before the date of IMP discontinuation and will be considered off-treatment otherwise.

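### A blank spasm count in a filled diary is scored as zero spasms, which lowers the exploratory 7-day average; the NRS formula and its prose need to be aligned

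*SAP*

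**What the plan says.** **Spasm count.** SAP 10.19 defines the 7-day average as total spasms divided by the number of days on which the diary was completed. It applies to the week before baseline and the weeks before Day 15 and D21 of each period. Two rules then deal with missing counts:

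- The weekly average is "set to missing if spasm counts are not collected during 4 days or more in total or for 3 consecutive days" in the 7-day window. SAP 10.2 has a similar rule for baseline.
- Where, on a given day, "the spasm count is missing whereas the eDiary has been filled by the patient, the number of spasms will be imputed to" zero for the purpose of deriving the average.

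The section does not say which rule is applied first. Appendix 14 describes the spasm count analysis as a model on observed values with no imputation. Its only supplementary versions are the per-protocol one and the one excluding COVID-19 impact.

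**NRS.** SAP 10.18 introduces the weekly value "as the mean NRS-spasticity score recorded in the eDiary during the last 7 days" before each timepoint. The displayed formula is "Sum of the NRS spasticity scores during the 7"-day window, divided by "Number of days in which the daily diary was completed during the 7"-day window. The average is "set to missing if scores are missing for 4 days or more in total or for 3 consecutive days". There is no zero-imputation paragraph. Appendix 14 again says observed values without imputation.

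**Status.** Protocol 13.6.4 lists both endpoints as exploratory. SAP 12.5.1 makes no multiplicity adjustment for them.

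**The concern.** Zero is the most favourable spasm count there is, and nothing in the SAP explains why an unanswered item should be read as a day without spasms. Because the day stays in the divisor, the blank acts as a reported good day rather than dropping out.

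This is out of line with the SAP's handling of other efficacy measures. An unperformed T25FW trial takes the worst value, 180 seconds, with a non-imputed analysis alongside (10.17). A missing LLMT response counts as failure (10.16). Blank MSSS-88 items take the mean of the completed items (10.20). Among these rules, only the spasm count gives a missing answer the best value, and no planned analysis takes the zeros out again.

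At stake are the level of the spasm endpoint, the size of its treatment difference and, if blanks are more common on one treatment, its direction. For the NRS, two programmers could follow the same section and obtain different averages if a diary can be submitted with that item empty.

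**Working it through.** The plan states no figure that rests on these rules, so there is nothing to reproduce; the formulas are worked through directly.

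**Inputs.** Numerator, divisor, zero rule and set-to-missing rule: SAP 10.19 and 10.18. Dependent variable and model terms: SAP 12.5.5.2 and 12.5.5.3. Assumed for illustration, not in the documents: 10 spasms on every answered day, NRS 6 on every answered day, and blank days that resemble answered days.

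**Step 1: effect on one weekly average.** Let all seven diaries be filled and *k* counts be blank.

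- As written: (sum of the 7 − *k* answers) / 7.
- Over answered days: (sum of the 7 − *k* answers) / (7 − *k*).
- Ratio: (7 − *k*)/7, a fall of *k*/7.

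| Blanks *k* | Fall *k*/7 | 10 spasms/day recorded as |
|---|---|---|
| 1 | 14.3% | 10 × 6/7 = 8.57 |
| 2 | 28.6% | 10 × 5/7 = 7.14 |
| 3 | 42.9% | 10 × 4/7 = 5.71 |

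A diary that was not filled at all causes no such shift: with two unfilled days the average is (5 × 10)/5 = 10. The effect is confined to blank items in filled diaries.

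**Step 2: how many blanks can get through.** The answer depends on whether an imputed zero counts as collected.

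- If it does not, at most three non-consecutive blanks pass. There are 35 ways to place three blanks in seven days; 5 of them are three in a row, which leaves 30. The largest fall is 42.9%.
- If it does, seven blanks in seven filled diaries pass, and the average is 0/7 = 0.

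**Step 3: effect on the treatment comparison.** The model uses the D21 weekly average itself, with treatment, period and sequence as fixed effects and no baseline term. With true means μN and μP and blanks kN and kP, the expected difference as written is μN(7 − kN)/7 − μP(7 − kP)/7.

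- Equal blanks *k*: the difference becomes (μN − μP)(7 − *k*)/7. With *k* = 2 it is 5/7, or 71%, of its true size.
- Unequal blanks with no true effect: at 10 spasms/day on both treatments, with two blanks on one and none on the other, the result is 7.14 − 10 = −2.86 spasms/day in favour of the treatment with the blanks.

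**Step 4: the NRS, side by side.** Under the prose, a blank is outside the mean and NRS 6 stays 6.00. Under the formula, a filled diary with a blank score adds nothing to the sum and one to the divisor, giving 5.14, 4.29 or 3.43 for one, two or three blanks. The two readings diverge only if such a diary can exist. SAP 10.8.2 does provide for "any day where the eDiary is filled but IMP dosing information are fully included or partial", but that concerns dosing items, not the NRS.

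**Step 5: Appendix 14 against 10.19.** Appendix 14 does declare component-level imputation where it applies: its primary T25FW entry states the 180-second single imputation at trial level. Its spasm entry says there is none. The zero rule in 10.19 therefore contradicts it.

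**The case against.** **The two spasm rules can be applied in order.** A blank count is one that was not collected, so the 4-day/3-consecutive-day rule could be run first and zeros used only in weeks that pass. This is a reasonable reading. A reader might infer that a week of blank counts is never set to missing, but the documents support that only if an imputed zero counts as collected, which they leave open. It is an ambiguity, and even the kinder reading lets through a 43% fall.

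**The NRS is not zero-scored.** A reader might infer from the divisor that blank NRS scores are treated as no spasticity. The documents do not establish this. Where the SAP wanted a zero it said so, 10.18 has no such paragraph, its prose refers to recorded scores, and its set-to-missing rule is already at item level. Nothing says the eDiary accepts a blank NRS. What stands is a conflict between formula and prose.

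**A blank may mean no spasms.** The documents do not describe the entry screen, so this cannot be ruled out, but nothing in them supports it and the SAP does not offer it as the reason.

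**The impact is limited.** This is correct. The endpoints are exploratory, each patient is compared with themselves, and the D21 average rather than change from baseline is modelled. Baseline and Day 15 averages are only summarised. A reader might also infer bias in favour of nabiximols; that needs more blanks on nabiximols, and no blank rates are given. None of this makes the zero rule right.

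**Conclusion.** The point holds for the spasm count. Followed as written, SAP 10.19 understates the 7-day average by one seventh for each blank in a week of seven filled diaries (14%, 29%, 43% for one, two, three), provided blank days resemble answered days. It contradicts Appendix 14 and leaves open whether a fully blank week is missing or averages zero. Equal blanking attenuates the treatment difference by (7 − *k*)/7; unequal blanking moves it toward the treatment with more blanks. How much this matters in practice depends on the blank rate, which is not given.

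For the NRS the conclusion is narrower: formula and prose conflict, and the result is affected only if a diary can be filled with that item empty. The primary and secondary efficacy endpoints are untouched. The change should be made before unblinding because it is cheap and the present rule has no stated justification.

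**What to change.** - SAP 10.19: delete the zero imputation, or keep it only as a labelled sensitivity analysis.
- SAP 10.18 and 10.19: divide each weekly average by the number of days with a non-missing answer to that item.
- Both sections: state that the existing 4-day/3-consecutive-day rule is applied to the item, before averaging, and that a blank item in a filled diary counts as missing. Use the same wording for baseline in SAP 10.2.
- Appendix 14: align the spasm count and NRS entries with the final derivations.

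The cost is SAP wording and one derivation change for each endpoint. The downside is small: a few more weekly averages may become missing.

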10.20 Multiple Sclerosis Spasticity Scale (MSSS-88)

The MSSS-88 will be completed at D21 of each period, and 8 sub-scales representing 8 domains along with a total score will be derived by summing each of the constitutive items provided that at least 50% of the items are answered. Missing responses will be replaced by the mean score of the items completed.

The questions will be grouped as follows:

- 3 spasticity specific symptoms
 - Muscle Stiffness: sum of questions 1 to 12,
 - Pain and Discomfort: sum of questions 13 to 21,
 - Muscle Spasms: sum of questions 22 to 35,
- 3 areas of physical functioning
 - Activity of Daily living (ADL): sum of questions 36 to 46,

- Ability to Walk: sum of questions 47 to 56,
- Body Movement: sum of questions 57 to 67,
- 2 area of psychosocial impact
 - Emotional health: sum of questions 68 to 80,
 - Social Functioning: sum of questions 81 to 88,
- Total score
 - Sum of the 8 non-missing sub-scales after missing data rule has been applied for each subscale, otherwise set to missing if any of the sub-scales is missing.

Table 10.20-1 Multiple Sclerosis Spasticity Scale - Missing Data Handling

Subscale and total score	Number of questions included in subscale and total score	Minimum number of questions required for score derivation (at least 50%)
Muscle Stiffness	12	6
Pain and Discomfort	9	5
Muscle Spasms	14	7
Activity of Daily living	11	6
Ability to Walk	10	5
Body Movement	11	6
Emotional health	13	7
Social Functioning	8	4

10.21 Adverse Events

10.21.1 Start and Stop Date Imputation

Table 10.21-1 Imputation Rules for Partial Adverse Events Start/Stop Dates

Parameter	Missing	Additional Conditions	Imputation
Start date for AEs	D	M and Y same as M and Y of first dose of study drug	Date of first dose of study drug
		M and/or Y not same as date of first dose of study drug	First day of month but should fall after 1st study drug intake or if impossible after informed consent date
	D and M	Y same as Y of first dose of study drug intake during period 1 and 2	Date of first dose of study drug
		Y after Y of first dose of study intake during Period 1 but same Y as 1 st study drug intake during Period 2	Date of first drug intake during period 2
		Y prior to Y of first dose of study drug but same as Y of informed consent date	Date of informed consent
		Y after Y of last study drug intake	The earliest date between date of last study drug intake + 14 days and end of study date
	D, M, Y	Not allowed by the system	Not applicable
Stop date for AEs	D	M and Y same as M and Y of last dose of study drug	The earliest date between date of last dose of study drug and end of study date
		M and/or Y not same as date of last dose of study drug	The earliest date between last day of month and end of study date
	D and M	Not allowed by the system	Not applicable
	D, M, Y	Not allowed by the system	Not applicable

AE = Adverse events; D = day; M = month; Y = year

Note: In all cases, if an estimated start date is after a complete stop date, use the first day of the stop date month.

Similarly, if the estimated stop date is before a complete or imputed start date, use the last day of the start date month.

10.21.2 COVID-19 AE

A confirmed or suspected COVID-19 AE will be any adverse event for which the AE term or the preferred term include the character “COVID-19” but should not be “COVID-19 ELISA test negative”.

For instance, confirmed COVID-19 TEAE will be reported as:

- COVID-19 infection,
- COVID-19 disease,
- COVID-19 pneumonia,
- COVID-19 respiratory infection,
- Asymptomatic COVID-19,

whereas suspected COVID-19 AE will be coded as Suspected COVID-19.

10.21.3 Time to First Onset of AE

The time to first onset of AE will be defined by study period as:

- AE start date – IMP start date in the studied period

For AEs with an onset date occurring during the 21-days on-treatment safety Period 1 (as defined in [Section 10.1.1](#)) the IMP start date refers to the date of 1st IMP spray intake during Period 1.

For AEs with onset date occurring during the 21-days on-treatment safety Period 2 (as defined in [Section 10.1.1](#)), the IMP start date refers to Period 2 start date provided that the patient is exposed during Period 2.

Based on the above value time to first onset of AE will be categorized as:

- 1-7 days,
- 8 to 14 days,
- 15 to 21 days,
- > 21 days.

If onset time is shorter as 1 day, it will be included in the 1-7 days category.

For the purpose of time-to-event analysis, censoring rules are defined in [Section 12.7.2.3](#).

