10.1.2 Reference Day and Study Day

The reference day (Day 1) will be the day of the first dose of study drug administration.

For a patient who was randomized but not exposed, the reference day date will be imputed by the randomization date.

The reference day for Period 1 (Period 1 Day 1) will be the reference day.

The reference day for Period 2 (Period 2 Day 1) will be the first day of IMP administration during Period 2. For a patient who entered the second period but was not exposed during this period, this reference day date will be imputed by the date of Visit 6 IRT call, if any, or the Visit 6 date.

The study day is defined relative to the reference day date. For assessments that occur after this visit date, the study day is calculated as (assessment date – reference day date + 1). For assessments that occur prior to first dose date, study day will be calculated as (assessment date – reference day date).

For the analyses being done by treatment arm, an **analysis day** will need to be derived for each treatment period as described in [Table 10.1-1](#). The analysis day is defined relative to the date of reference day of each study period.

For assessments that occur prior to reference day date, analysis day will be calculated as (assessment date – reference day date);

For assessments that occur on or after the Period 1 reference day date until the end of the wash-out period, analysis day will be calculated as (assessment date – Period 1 reference day date +1);

For assessments that occur on or after Period 2 reference day date the analysis day will be calculated as (assessment date – Period 2 reference day date +1);

Thus, there is no study day or analysis day referring to Day 0.

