12.3.1.2 IMP Dosing

Patients are expected to record, daily, the number of morning and evening spray(s) they have taken in their eDiary. This information will be integrated in the eCRF.

At Day 15 of each treatment period (at the end of the titration phase), the daily number of sprays to be taken by each patient defined as the optimized dose will be reported in the eCRF “Dose adjustment” form.

Whenever a patient has taken an amended dose, this will also be reported in the eCRF "Dose adjustment" form along with start and stop date of each amended dose and the reason why the optimized dose was amended (e.g., adverse event, insufficient therapeutic effect, other).

During the Titration Phase (up to Day 14)

The number of sprays taken will be summarized by day as quantitative variable (n, mean, SD, median, Q1, Q3, min and max) but also presenting per day, the number of sprays administered as a categorical variable.

Additionally,

- the rate of missing diary day information (%),
- the patient percentage of imputed diary days (%),
- the patient total number of daily sprays,
- the patient mean number of daily sprays,
- the patient mode number of daily sprays,
- the patient median number of daily sprays,
- the rate of "0" total daily sprays (%),
- the rate of ">12" total daily sprays (%),

as defined in [Section 10.8.2](#) and [Section 10.9](#), will be summarized per treatment arm as quantitative variable (n, mean, SD, median, Q1, Q3, min and max).

During the Maintenance Phase (Day 15 to D21)

As defined in [Section 10.8.2](#),

- the patient total number of daily sprays,
- the patient mean number of daily sprays,
- the patient mode number of daily sprays,
- the patient median number of daily sprays

Combined: During the Titration Phase (up to Day 14) + Maintenance Phase (Day 15 to D21)

- the rate of "0" total daily sprays (%),
- the patient maximal number of daily sprays

will be summarized as quantitative variable (n, mean, SD, median, Q1, Q3, min and max).

In addition, the patient mean number of daily sprays used by patient will be categorized as ≤ 6 sprays; > 6 to ≤ 12 sprays and >12 sprays and summarized.

As defined in [Section 10.9](#),

- the rate of missing diary day information (%),
- the patient percentage of imputed diary days (%),
- the rate of "0" total daily sprays (%),
- the rate of >12 total daily sprays (%)

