12.7.1.2 All-causality Treatment-emergent Adverse Event Summary

Descriptive presentations of TEAEs will be given by PT and SOC for the Safety Analysis Set. The number and percentage of patients reporting at least one TEAE within a given treatment arm will be provided as described below

- *All TEAEs by SOC and PT,
- *All TEAEs by SOC, PT and subgroups (as described in Table 12.7-1),
- Most common TEAEs (incidence $\geq 5\%$ in either treatment arm) by SOC and PT,
- Most common TEAEs (incidence ≥ 2 patients in either treatment arm) by SOC and PT,
- Most common TEAEs (incidence ≥ 2 patients in either treatment arm) by SOC, and PT and subgroups (as described in Table 12.7-1),
- All TEAEs by SOC, PT and maximum severity,
- All TEAEs by SOC, PT and worst action taken on study drug,
- All TEAEs by SOC, PT and time of first onset of AE categorized as:
1-7 day, 8 to 14 days, 15 to 21 days and > 21 days (as described in [Section 10.21.3](#)),
- All TEAEs by SOC, PT and AE duration, categorized as:
1-7 day, 8 to 14 days, 15 to 28 days, 29 to 42 days, 43 to 61 days, > 61 days, ongoing, indeterminate (as described in [Section 10.21.4](#)),
- All TEAEs by SOC, PT and relationship to IMP,
- All treatment-related TEAEs by SOC and PT and maximum severity,
- *All treatment-related TEAEs by SOC and PT and subgroups (as described in Table 12.7-1),
- *All treatment-related TEAEs leading to permanent IMP discontinuation by SOC and PT,
- *All TEAEs leading to permanent IMP discontinuation by SOC and PT,
- *All TEAEs leading to permanent IMP discontinuation by SOC and PT and subgroups (as described in Table 12.7-1),
- All treatment-related TEAEs leading to permanent IMP discontinuation by SOC and PT and maximum severity,
- All non-serious TEAEs by SOC and PT,
- All most common non-serious TEAEs (incidence $\geq 5\%$ in either treatment arm) by SOC and PT.

**These tables will also present the total number of AEs by treatment arm and as appropriate by category of subgroup.*

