12.7.2.3 Adverse Events of Special Interest

An adverse events of special interest (AESI) is any adverse event of scientific or medical interest to the study medication. The types of AESIs which will be analyzed are presented in **Descriptive presentations of AESIs** will be given for each AESI category on the safety analysis set presenting:

- The number and percentage of patients with at least one treatment-emergent AESI,
- The number and percentage of patients with at least one treatment-emergent AESI by SOC and PT,
- The number and percentage of patients with at least one severe treatment-emergent AESI,
- The number and percentage of patient with at least one serious treatment-emergent AESI,
- The number of and percentage of patients with at least one treatment-emergent AESI leading to permanent IMP discontinuation,
- The number of treatment-emergent AESI,
- The number of severe treatment-emergent AESI,
- The number of serious treatment-emergent AESI,
- The number of treatment-emergent AESI leading to permanent IMP discontinuation,
- The number of unique* treatment-emergent AESI,
- The number of unique* severe treatment-emergent AESI,
- The number of unique* serious treatment-emergent AESI,
- The number of unique* treatment-emergent AESI leading to permanent IMP discontinuation,
- The time to first onset of treatment-emergent AESI categorized as :1-7 day, 8 to 14 days, 15 to 21 days, 21 to 28 days and > 28 days (as described in [Section 10.21.3](#)),

**Unique AESI is defined as any AESI coded with the same PT and having the same date of onset.*

Analysis of time to first onset of AESIs will be conducted by actual treatment arm on the Safety Analysis SAS using the SAS® LIFEEST procedure.

Assuming no carry over effect, Kaplan-Meier plots (estimates) of cumulative incidence of first onset of AESI will be provided by actual treatment arm on the Safety analysis set. The time to AESI onset (in days) is defined as the number of days from 1st IMP intake of the treatment arm (e.g., nabiximols, placebo) the AESI is emergent to (as defined in [Section 12.7.1](#)) until the onset of the AESI (see detailed in [Section 10.21.4](#)).

For patients not known to have experienced an AESI during respectively Period 1 and Period 2:

- Period 1 censoring day is the date of 1st IMP intake during Period 2 minus 1 day for those patients continuing in Period 2 and, the end of study date for those patients who discontinued before Period 2,

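### SAP 10.21.3 counts AE onset time without the +1 used for study day, so the 1–7 day bin spans eight study days; separately, the AESI onset bins in 12.7.2.3 overlap at 21

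*SAP*

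**What the plan says.** SAP 10.21.3 computes time to first onset, separately by period, as "AE start date – IMP start date in the studied period". It sorts the result into 1–7, 8–14, 15–21 and >21 days and adds: "If onset time is shorter as 1 day, it will be included in the 1-7 days category". SAP 12.7.1.2 repeats the same four bins for the table of all TEAEs by SOC, PT and onset time.

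The day numbering is set in SAP 10.1.2: "The reference day (Day 1) will be the day of the first dose of study drug administration". After dosing, the "analysis day will be calculated as (assessment date – Period 1 reference day date +1"), and the same rule applies in Period 2. The section concludes: "Thus, there is no study day or analysis day referring to Day 0". Time to treatment discontinuation (10.6), exposure duration (10.7) and AE duration (10.21.4) are also date differences plus 1. The exposure table in 12.3.1.1 uses the same cut points as the onset bins, but as study days: Day 1 to 7, 8 to 14, 15 to 21 and beyond Day 21.

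For adverse events of special interest, SAP 12.7.2.3 cites 10.21.3 for the onset categories but ends its list with "15 to 21 days, 21 to 28 days and > 28 days".

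**The concern.** The onset formula gives 0 for an event on the first dosing day. The bins start at 1 and have the same limits as the Day-1-based exposure categories. The below-1-day rule moves the zero into the first bin and leaves every other value where it is. The labels therefore do not describe the study days that the bins contain, and the first bin is a day wider than the next two.

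At stake is how the onset-interval tables read. Someone comparing the onset table with the exposure table, or with study days in a listing, would find the same labels covering different days. The wider first bin also tilts the table towards early onset. The percentages use the patients at risk in each interval as denominator (SAP 12.7.1), which does not adjust for the length of the interval.

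The AESI list is a separate defect. A value of 21 belongs to two categories, and the list differs from the section it cites.

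**Working it through.** **Inputs.** The onset formula, bins and below-1-day rule come from SAP 10.21.3. Day 1 as the first dosing day and the +1 for analysis day come from SAP 10.1.2.

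**Conversion.** Days elapsed since first dose = study day − 1. The protocol's own figures reproduce:

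- Day 8 is 7 days after first dose (Protocol 9.1.2.2)
- Days 15 and 21 are 14 and 20 days after (9.1.2.3)
- Day 31 is 30 days after (9.1.4.1)
- Days 45 and 51 are 44 and 50 days after (9.1.4.3)

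**Assigning each study day of a period to a bin:**

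| Bin label | Date differences it takes | Study days as written | Width | Study days with +1 | Width |
|---|---|---|---|---|---|
| 1–7 days | 0–7 | 1–8 | 8 | 1–7 | 7 |
| 8–14 days | 8–14 | 9–15 | 7 | 8–14 | 7 |
| 15–21 days | 15–21 | 16–22 | 7 | 15–21 | 7 |
| >21 days | 22 on | 23 on | open | 22 on | open |

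Over Days 1–30 of a period, exactly three days change bin when 1 is added: Days 8, 15 and 22. On the nominal schedule, with Period 2 starting on Day 31, these are trial Days 38, 45 and 52 in that period. With +1 the bins agree with the exposure categories of 12.3.1.1.

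**Size, for illustration.** Assume onsets are uniform over Days 1–21. The bins as written then hold 8, 7 and 6 of the 21 days (Days 1–8, 9–15 and 16–21):

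- 8/21 = 38.1%
- 7/21 = 33.3%
- 6/21 = 28.6%

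With +1, each bin holds 7/21 = 33.3%. In width alone, the first bin has one extra day in seven (1/7 = 14%). The documents give no onset distribution, so these figures show direction and scale only.

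**AESI bins.** The list 15–21, 21–28, >28 assigns the value 21 twice. This is true with or without the +1, so the change to the formula does not cure it.

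**The case against.** Time to onset can properly be measured as elapsed time. SAP 12.7.2.3 reports Kaplan-Meier estimates at 7, 14, 21 and 28 days after first intake, and the protocol counts its visits in elapsed days. The onset bins are written as days rather than as Day 1 to Day 7, and 10.21.3 says where the zero goes, so the rule can be programmed. A similar sentence for durations under 1 day appears in 10.21.4, where the +1 is used, so that sentence is weak evidence of a slip.

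Part of this stands. An elapsed-day convention is coherent, but the SAP would have to state it and label the first bin 0–7, which would still be eight days wide. The SAP's own practice also points the other way: 12.1 describes time to treatment discontinuation as days from first intake, and the formula for it in 10.6 adds 1.

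Two further objections stand. The rule is the same for both treatments, so it introduces no differential handling of nabiximols and placebo. The uniform-onset figures are an assumption, and in a trial that titrates from a single spray, onsets need not be uniform.

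A reader might infer more than the documents support:

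- **That maintenance events are shown as titration events.** SAP 12.3.1.2 does head one summary "During the Maintenance Phase (Day 15 to D21"), but no onset bin carries a phase label. SAP 10.8.1 sets the phases by visit and dosing dates, and Protocol 9.1.2.3 allows ±1 day for Visit 4 and ±2 days for Visit 5. If Visit 4 falls on Day 16, Day 15 is still titration, and adding 1 would put it in the 15–21 bin. If Visit 5 falls on Day 22 or 23, Day 22 is a dosing day, and adding 1 would put it in the >21 bin. Fixed-day bins cannot represent phases under either convention.
- **That Day 22 events are wrongly treated as on treatment.** For AEs, the on-treatment safety period in SAP 10.1.1 already extends past the last dose by up to 14 days, and SAP 12.7.1 links washout events to the Period 1 treatment. Adding 1 changes neither.
- **That every other day count in the SAP adds 1.** Pre-dose study and analysis days in 10.1.2 do not.

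**Conclusion.** The point holds as a minor correction. As written, the 1–7 day bin covers eight study days, and events on Days 8, 15 and 22 of a period fall one bin earlier than their study day and than the matching exposure category. That follows from the SAP's formula and day numbering without further assumption. The shift to 38.1%, 33.3% and 28.6% holds only under uniform onset over Days 1–21. The overlap at 21 in 12.7.2.3 is an error under either reading of the formula.

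The effect is confined to the descriptive onset-interval tables and their at-risk denominators. TEAE status, attribution to treatment arm, overall incidence and all hypothesis tests are unchanged. The documents do not support presenting this as a confusion of titration, maintenance and off-drug events.

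**What to change.** - In SAP 10.21.3, define time to first onset as AE start date minus IMP start date in the period, plus 1. Remove the sentence on onset times shorter than 1 day; an event on the first dosing day then scores 1, so the rule is not needed.
- In SAP 12.7.2.3, replace the end of the list with 15–21, 22–28 and >28 days. The last two together equal the >21 category of 10.21.3, so the AESI table stays consistent with 10.21.3 and 12.7.1.2.
- State the day count for the Kaplan-Meier onset times in 12.7.2.3. For detail, that text points to 10.21.4, which defines AE duration, not onset.
- Do not describe the bins as titration, maintenance or off-drug phases. A summary by phase would need the visit and dosing dates in 10.8.1.

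The cost is a few words in the SAP, one line of derivation code and one corrected table shell. No data collection changes.
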